### **15.0. Early Termination or Suspension of the Investigation**

The Sponsor reserves the right to terminate/suspend the extended study at any point should they believe that important harmful events might result from its continuation. Study patients may withdraw from the extended study at any time without penalty or loss of benefits. The investigator may also decide to withdraw a patient from the extended study at any time on the basis of medical judgement. In any case, the reasons for withdrawal will be documented.

## **16.0. Publication Policy**

Publication policy, rights and obligations for this Investigation have been negotiated, detailed and defined in the Investigation Contractual Documents and Agreements with the Investigation Site and Investigators.

## **17.0. Data Collection**

All data will be recorded on standardized, preprinted, data collection forms (CRF) suitable for electronic data capture. Data will be entered by qualified personnel (i.e., the clinical investigator or a person designated by him/her).

## **18.0. Data Reporting**

Progress reports and a final report at the conclusion of the clinical investigation will be submitted by the investigators and Sponsor to the regulatory bodies and local IRB/ethics committees as required by local regulations.

---

**ATTACHMENT A**  
**Written Procedures for Monitoring Investigations**

---

**Written Procedures for Monitoring Investigations**

**A. Selection of the monitor.**

Designated by the sponsor to oversee the extended investigation, the monitor must be an employee of the sponsor or an independent contractor or consultant. The monitor shall be qualified by training and experience to monitor the investigational study in accordance with all applicable regulations and standards for conducting clinical investigations.

**B. General duties of the monitor.**

The monitor must ensure that the extended investigation is conducted in accordance with:

1. The signed investigator agreement.
2. The clinical investigational plan (CIP)/protocol.
3. Any conditions imposed by the IRB/EC or regulatory authority.
4. The requirements of the applicable regulations and standards.

**C. Reports by the monitor to the sponsor.**

1. Any noncompliance with the items listed above. In the event that the investigator is not complying with the requirements outlined above, it is the sponsor's responsibility to secure compliance.
2. Any adverse events/effects that are potentially reportable to a regulatory authority.

**D. Initiating the study.**

Prior to initiating any clinical use of the device, the monitor must conduct a pre-investigation or initiation visit with each investigator to ensure that:

1. The investigator understands the investigational status of the device.

2. The investigator understands and accepts his/her obligation in conducting the extended clinical investigation.
3. The investigator and his/her staff have sufficient time and access to an adequate number of subjects to conduct the extended clinical investigation.
4. The investigator has a signed Investigator Agreement on file.
5. Each IRB/EC approval is on file, and all conditions of the IRB/EC approval have been met.
6. The clinical use of the device does not begin until regulatory authority and IRB/EC approval has been received.

E. During the course of the extended investigation.

1. Conduct periodic discussions with the investigator or his/her staff to ensure that the study is being conducted in accordance with the protocol or Clinical Investigational Plan, any conditions of the IRB/EC, and the requirements of the applicable regulations.
2. Review study data sheets (i.e., paper or electronic case report forms, data collection forms) and records to ensure that they are complete, accurate, and legible.
3. Review study data sheets (i.e., paper or electronic case report forms, data collection forms) and records for any adverse events/effects that are potentially reportable to a regulatory authority.
4. Ensure that the investigator has properly disposed of or returned all devices to the sponsor, unless this action would jeopardize the rights, safety, or welfare of the subject.

F. Records of the monitor.

The monitor shall prepare and maintain records of each initiation visit and each periodic visit, general site contact, or discussion. These will include:

1. Date, name and address of the investigator, and names of other staff members present at each meeting.
2. A summary of the findings of the visit.
3. A statement of any action taken by the monitor or investigator to correct any deficiencies noted.
4. The monitor shall immediately notify the sponsor of any conditions of non-compliance with the protocol, Clinical Investigational Plan,

conditions of IRB/EC or regulatory authority approval, or the applicable regulations.

---

## ATTACHMENT B

### Definitions

---

#### **Definitions**

*Aneurysm (common iliac artery):* > 20 mm in diameter (outer wall to outer wall).

*Aneurysm (internal iliac artery):* > 20 mm in diameter (outer wall to outer wall).

*Buttock Claudication:* Pain in the buttock or posterior thigh, which is initiated by activity and resolves with rest.

*Calcification:* Calcification will be graded based upon the following:

None:	Lack of calcification.
Mild:	Less than 40% circumferential calcification.
Moderate:	40-70% circumferential calcification.
Severe:	Greater than 70% circumferential.

*Embolization:* Clinical evidence of ischemic tissue remote from the operative field, presumably caused by thrombus dislodged from the aneurysmal sac, aortic neck, or adjacent vessels, including ischemia of the kidneys, pelvis (IIA), or lower limbs. This is, of course, distinct from pre-operative, operative or post-operative intentional embolization procedures.

*Endoleak:* Contrast-enhanced blood entering the aneurysm sac from around the proximal or distal end of the graft (type I), between joints of the graft and extension (if applicable) or through defects in the graft material (type III), via collateral vessels (type II), or graft fabric porosity (type IV).

*Endoleak Type Classification:*

*Type I endoleak:* A peri-prosthetic leak occurring at the proximal and/or distal attachment zones of the endovascular system.

*Type II endoleak:* A leak caused by retrograde flow from patent vessels.  
(Requires imaging documentation of Type II source). To classify an endoleak as

*Type II*, documentation with a CT-enhanced and/or selective angiogram clearly showing the source is required.

*Type III endoleak*: A leak caused by a defect in the graft fabric, inadequate seal (between graft components only), or disconnection of additional or ancillary graft components.

*Type IV endoleak*: A leak caused by graft fabric porosity, often resulting in a generalized blush of contrast within the aneurysm sac.

*Unknown endoleak*: Continuing blood flow into the aneurysmal sac with undefined origin.

*Endoleak (early)*: Any endoleak observed by core laboratory within 30 days of device deployment.

*Endoleak (late)*: Any endoleak observed by core laboratory later than 30 days after device deployment, which was not documented during the first 30 days post-deployment.

*Ileus*: Absence (or lack) of intestinal peristalsis lasting more than 4 days.

*Limb Occlusion (Branch Graft)*: Core laboratory determination of the presence of thrombus within any aspect Zenith® Branch Endovascular Graft-Iliac Bifurcation (i.e., common iliac segment, external iliac segment, or sidebranch segment), creating occlusion.

*Lower Extremity Ischemia*: New tissue loss or rest pain.

*Major Complications*: Conversion to open surgical repair, aneurysm rupture, death, any cardiac events requiring percutaneous or surgical intervention, renal failure requiring dialysis where not previously needed, bowel ischemia, new onset of impotence or buttock claudication on the same side as Branch Graft implantation, ileus, lower extremity ischemia, ischemic neuropathy, paralysis, and stroke.

*Medically Intractable Hypertension*: Systolic arterial pressure >160 mmHg despite receiving medication.

*MI (Non-Q-Wave)*: Investigator identified patients having clinical evidence of a myocardial infarction with elevated peak CK values greater than or equal to three times the upper limit of normal with elevated CK-MB (above the institution's upper limit of

normal) in the absence of new pathological Q-waves or clinical evidence of a myocardial infarction with troponin greater than three times the upper limit of normal, as determined by the investigator.

*MI (Q-Wave):* Post-procedure presence of new Q-waves greater than 0.04 seconds in at least two EKG leads.

*Migration-Radiographic (Branch Graft):* Core laboratory determination, and CEC confirmation, of caudal or cranial movement of the Branch Graft  $\geq 10$  mm relative to the overlap with the iliac leg graft (TFLE/ZSLE) as compared to the position on the first post-operative CT scan.

*Migration-Clinical (Branch Graft):* Antegrade or retrograde movement of the Branch Graft requiring surgical or endovascular intervention.

*Morbidity Index:*

Category	Measured Element
Cardiovascular	1) Q-wave myocardial infarction 2) non-Q-wave myocardial infarction 3) congestive heart failure (CHF) 4) arrhythmias which require new medication or treatment 5) cardiac ischemia requiring intervention 6) inotropic support 7) medically intractable hypertension
Pulmonary	8) reintubation or ventilation $> 24$ hours 9) pneumonia requiring antibiotics 10) patient receiving supplemental oxygen at discharge
Renal	11) dialysis in patients with normal pre-operative renal function 12) creatinine rise $> 30\%$ from baseline on two or more follow-up tests
Bowel	13) bowel obstruction 14) bowel ischemia 15) paralytic ileus $> 4$ days
Access Site/Incision	16) infection requiring antibiotic treatment 17) hernia 18) lymph fistula 19) dehiscence 20) necrosis requiring debridement
Neurologic	21) stroke 22) TIA 23) spinal cord ischemia/paralysis
Vascular	24) buttock claudication on the same side as Branch Graft implantation 25) limb thrombosis on the same side as Branch Graft implantation 26) distal embolization resulting in tissue loss or requiring intervention 27) transfusion post procedure (resulting from pseudoaneurysm, vascular injury, aneurysm leak or other procedure related causes) 28) pseudoaneurysm

Category	Measured Element
	29) aorto-enteric fistula 30) vascular injury (such as inadvertent occlusion, dissection or other procedure related causes) 31) aneurysm leak or rupture 32) increase in aneurysm size by more than 0.5 cm relative to the smallest of any prior measurement.
Miscellaneous	33) impotence

*New York Heart Association Classification:*

- 1 Patient with cardiac disease but without resulting limitations of physical activity. Ordinary physical activity does not cause undue fatigue, palpitation, or dyspnea.
- 2 Patients with cardiac disease resulting in slight limitation of physical activity. They are comfortable at rest; ordinary physical activity results in fatigue, palpitation or dyspnea.
- 3 Patients with cardiac disease resulting in marked limitation of physical activity. They are comfortable at rest; less than ordinary physical activity causes fatigue, palpitation or dyspnea.
- 4 Patients with cardiac disease resulting in inability to carry out any physical activity without discomfort. Symptoms of cardiac insufficiency may be present even at rest. If any physical activity is undertaken, discomfort is increased.

*Occlusive Disease of Iliacs:* Occlusive disease will be graded based upon the following:

None:	Lack of occlusive disease.
Mild:	Some disease, focal with less than 30% narrowing.
Moderate:	Between 30-50% narrowing not requiring interventional techniques to meet inclusion criteria.
Severe:	Greater than 50% or any patient requiring angioplasty prior to endograft delivery.
100% Occluded:	No blood flow past site of occlusion.

*Patency-Related Intervention:*

- Secondary intervention to treat a > 60% stenosis of the internal iliac artery (as identified through CT, angiography, or duplex ultrasound and confirmed by core laboratory) associated with clinical symptoms. Of note, this not only includes patients with internal iliac artery stenosis following successful placement of the Zenith® Branch Endovascular Graft-Iliac Bifurcation and covered bridging stent, but also any cases of technical failure resulting in occlusion of the internal iliac

artery during the initial implant procedure that require secondary intervention for associated clinical symptoms.

*Renal Failure:* Acute or progressive renal insufficiency leading to the need for dialysis or hemofiltration.

*Renal Insufficiency:* A rise in serum creatinine of more than 30% above the pre-procedure level, resulting in a serum creatinine level  $> 2.0$  mg/dl that does not spontaneously resolve (does not include those patients with a pre-procedure serum creatinine  $> 2.0$  mg/dl).

*Serious Adverse Event:* An adverse event that led to death, led to a serious deterioration in the health of the subject that resulted in a life-threatening illness or injury, resulted in a permanent impairment of a body structure or a body function, required in-patient hospitalization or prolongation of existing hospitalization, resulted in medical or surgical intervention to prevent permanent impairment to body structure or a body function, led to fetal distress, fetal death, a congenital abnormality or birth defect.

*Stent/attachment system fracture/break:* Fracture or breakage of any portion of the Zenith® Branch Endovascular Graft-Iliac Bifurcation or covered bridging stent or attachment system including metallic fracture or breakage of any suture material used to construct the stent or secure the stent or attachment system to the graft material as determined by the core laboratory and confirmed by CEC.

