#### 4.3.2. Secondary Safety Hypothesis

The secondary safety hypothesis will assess the freedom from 30-morbidity and will be based on results from the cohort of patients treated with the Zenith® Branch Endovascular Graft-Iliac Bifurcation in combination with the Atrium iCAST™ covered stent as part of the extended study. For the secondary safety endpoint performance goal, patients with occluded internal iliac arteries in the Zenith® AAA Endovascular Graft Clinical Study were evaluated to identify the rate of 30-day morbidity based on a composite endpoint of

---

31 pre-specified measured elements in seven categories (i.e., cardiovascular, pulmonary, renal, bowel, wound, neurologic, and vascular) which comprised the morbidity index for the Zenith® AAA Endovascular Graft Clinical Study. Approximately 44% of the patients had experienced morbidity within 30 days, with a margin of 10%, a performance goal of 46% was established. [The information in this section has been redacted due to confidential content.]

The null ( $H_0$ ) and alternate ( $H_A$ ) hypotheses are expressed as follows:

Null Hypothesis: The rate of freedom from 30-day morbidity following treatment with the Zenith® Branch Endovascular Graft-Iliac Bifurcation does not meet the performance goal (46%).

$$H_0: p \leq 46\%$$

Alternate Hypothesis: The rate of 30-day morbidity following treatment with the Zenith® Branch Endovascular Graft-Iliac Bifurcation meets the performance goal (46%).

$$H_A: p > 46\%$$

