## 8.10. Statistical Considerations

### 8.10.1 Sample Size

Bayesian simulation studies were performed to determine the sample size required to test the study hypotheses with sufficient statistical power (in the frequentist context).

For the power calculation of the primary hypothesis, the true patency rate of the IIA following treatment with the Branch Graft was assumed to be 83% based on the literature. With a performance goal of 55% for freedom from patency-related intervention (derived as described in section 4.3.1), the simulation study indicates that a maximum sample size of 25 patients will provide a power of approximately 88.5%, at a type I error rate of 2.5%.

For the secondary safety hypothesis, the true rate of freedom from 30-day morbidity was assumed to be 72.5%, which was derived from patients with patent internal iliac arteries in the Zenith® AAA Endovascular Graft Clinical Study who were free from 30-day morbidity (i.e., free from all 31 events in the Zenith® AAA Endovascular Graft Clinical Study morbidity index and hip/thigh/buttock claudication). With a performance goal of 46% for freedom from 30-day morbidity (derived as described in section 4.3.2), the simulation study indicates that a maximum sample size of 29 patients will provide a power of 85.8%, at a type I error rate of 2.5%.

---

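### Morbidity index element 25 counts limb thrombosis only on the Branch Graft side, so on this one element the trial is very probably narrower than the historical index behind its 46% goal

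*Protocol*

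**What the plan says.** Attachment B lists the Morbidity Index as 33 numbered elements. Two vascular elements carry a side limit: element 24, "buttock claudication on the same side as Branch Graft implantation", and element 25, "limb thrombosis on the same side as Branch Graft implantation".

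Section 4.3.2 gives the source of the goal: "patients with occluded internal iliac arteries in the Zenith® AAA Endovascular Graft Clinical Study were evaluated to identify the rate of 30-day morbidity". The composite used was "31 pre-specified measured elements in seven categories", "which comprised the morbidity index for the Zenith® AAA Endovascular Graft Clinical Study". The goal follows: "Approximately 44% of the patients had experienced morbidity within 30 days, with a margin of 10%, a performance goal of 46% was established".

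Section 8.10.1 takes its planning rate of 72.5% from a different group of the same study, patients with patent internal iliac arteries. They had to be free of all 31 events in that study's "morbidity index and hip/thigh/buttock claudication". No side is stated there.

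Section 8.11.2 (Additional Component Sizing) says that the repair includes a standard AAA graft with main body and iliac legs.

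**The concern.** A single-arm test against a fixed historical goal is fair only if the trial counts the same events as the source of the goal. A thrombosed limb opposite the Branch Graft would probably have been a failure in the benchmark. Here it is not counted under element 25. Most other elements, such as pneumonia, hernia or transfusion, apply to the whole patient or procedure. Only elements 24 and 25 are limited to one side, and the protocol as shown gives no reason.

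Narrowing an element raises the observed freedom from morbidity without any change in patient outcome. Taken alone, that makes the goal easier to meet.

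**Working it through.** **1. The goal.** Section 4.3.2: 100 − 44 − 10 = 46%. This agrees with the stated figure.

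**2. Was limb thrombosis among the historical 31?** The Attachment B elements by category are: cardiovascular 7, pulmonary 3, renal 2, bowel 3, access site/incision 5, neurologic 3, vascular 9, miscellaneous 1.

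- Total: 7 + 3 + 2 + 3 + 5 + 3 + 9 + 1 = 33.
- Impotence (33) sits in a miscellaneous category that is not among the seven named in Section 4.3.2.
- Claudication (24) is named in Section 8.10.1 as additional to the 31.
- 33 − 2 = 31, which matches the historical count. The remaining categories match the historical seven, if access site/incision is taken as the category that Section 4.3.2 calls wound.

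Limb thrombosis is among the 31 that remain. Its side limit refers to a device that the earlier study, as described, did not use. The limit was therefore evidently added for this trial. This count identifies the element; it does not show how the element was counted historically.

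**3. The plan's own power figure.** The rule is to pass if the 2.5th posterior percentile exceeds 0.46. The prior is not given in the text shown, so a flat prior is assumed: posterior Beta(1 + r, 1 + n − r) for r successes in n patients.

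- n = 29: the percentile is 0.439 at r = 18 and 0.472 at r = 19, so 19 or more pass.
- Power at 72.5%: P(X ≥ 19 | 29, 0.725) = 85.3%, against 85.8% stated. Reproduced closely.
- Chance of passing at 46%: P(X ≥ 19 | 29, 0.46) = 2.7%, against 2.5% stated.
- n = 40 (the planned cohort): the percentile is 0.445 at r = 24 and 0.469 at r = 25, so 25 or more pass.

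A Jeffreys prior gives the same two thresholds.

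**4. Sensitivity to the side limit.** The protocol gives no rate of limb thrombosis. Let d be the assumed share of patients whose only index event by day 30 is a contralateral limb thrombosis. If true freedom under any-limb counting is 46%, freedom under the trial definition is 46% + d. The chance of passing is P(X ≥ r | n, 0.46 + d):

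| d (assumed) | Expected patients in 40 | n = 29, r = 19 | n = 40, r = 25 |
|---|---|---|---|
| 0 | 0 | 2.7% | 2.7% |
| 0.5% | 0.2 | 3.1% | 3.1% |
| 1% | 0.4 | 3.5% | 3.5% |
| 2% | 0.8 | 4.4% | 4.7% |
| 3% | 1.2 | 5.5% | 6.0% |

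These figures include no offset from the elements that the trial added.

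**5. How plausible is the range?** d counts sole events only. If contralateral thrombosis is independent of the other events, its total rate is d divided by the freedom from all other events: 0.01/0.47 = 2.1% for d = 1%, and 0.03/0.49 = 6.1% for d = 3%. Nothing in the protocol supports the upper end.

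**The case against.** **The historical wording is not shown.** Section 4.3.2 gives only the number of elements and the categories, and text after the goal is redacted. The benchmark group had occluded internal iliac arteries, and the protocol does not say whether their limb events were counted on any side or only on the occluded side. This stands. It makes the narrowing a strong inference rather than an established fact, and the fix is conditional for that reason.

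**The trial index is also wider.** It adds claudication and impotence, which make the goal harder to meet. Section 4.3.1 puts pelvic ischemic symptoms at about 45% when the artery is sacrificed, so claudication may not be a trivial addition even if preservation lowers it. This stands. A reader might infer that the safety test as a whole is lenient; the protocol does not support that, because the net direction is unknown. Offsetting mismatches still do not make a like-for-like test.

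**Other elements may catch contralateral events.** Elements 26 (distal embolization resulting in tissue loss or requiring intervention) and 30 (vascular injury, including inadvertent occlusion) have no side limit. This stands in part: it shrinks the effect but does not cover every limb thrombosis.

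**The limit may be deliberate.** Attachment B defines limb occlusion for the Branch Graft only, and Section 8.3 acknowledges difficulty in attributing events to components. Same-side counting is a sound choice for a device-specific result. It does not suit a comparison with an index that could not have been limited to that side.

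**Element 24.** Its side limit might tempt a reader to widen it in the same way. That would not help the test against 46%: claudication is, by Section 8.10.1, outside the 31 elements behind the goal, so widening it would move the trial further from the benchmark. The claudication definition without a stated side belongs only to the 72.5% planning rate.

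**Conclusion.** The point holds for element 25. The trial definition is very probably narrower than the historical element behind the 46% goal. This rests on the count of 33 − 2 = 31 and on the earlier study having had no Branch Graft, as the protocol describes it.

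The effect is probably small and cannot be sized from the protocol. With 40 patients, a flat prior and an assumed sole-event rate of 0.5% to 3%, the chance of passing at a true 46% rises from 2.7% to between 3.1% and 6.0%, before any offset. This is a sensitivity range, not an estimate of the trial's type I error. It is a minor, worthwhile correction and does not invalidate the safety test.

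**What to change.** For the test against 46%, count element 25 in any graft limb, unless the sponsor shows that the historical count was limited by side. Report the count for the Branch Graft side only as the supportive, device-specific result. At minimum, keep the present definition, state how the historical element was counted, and add a sensitivity analysis that counts limb thrombosis on either side.

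Leave element 24 as it is for this test. Separately, reconcile it with the hip/thigh/buttock claudication used for the 72.5% planning rate in Section 8.10.1, which has no stated side limit.

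The cost is a wording change to one element. Little new data collection should be needed: complications go on an event form (Section 8.8), and CT is scheduled at month 1 (Table 8.8-1). The case report forms are not shown, however, and the core laboratory's limb occlusion definition covers only the Branch Graft, so capture of contralateral events should be confirmed. The downside is that a contralateral event not caused by the Branch Graft can count as a failure. The supportive same-side result makes such cases visible.

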##### **4.1. Primary Objectives**

Primary Endpoint: The primary assessment will be based on 6-month freedom from patency-related intervention since the Zenith® Branch Endovascular Graft-Iliac Bifurcation is intended to maintain blood flow to the internal iliac artery and minimize the risk of associated clinical symptoms with the need for reintervention.

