#### *Success Measures*

- *Technical Success:* The ability to deliver and deploy the Zenith® Branch Endovascular Graft-Iliac Bifurcation and covered bridging stent in the desired location; graft patency and internal iliac artery patency following deployment, as evidenced by intraoperative angiography; and successful removal of the delivery system.
- *Procedural Success:* Technical success with no type I, type III, or type IV endoleaks (see endoleak definition) at 30 days; no procedure-related major complications through 30 days; freedom from patency-related intervention through 30 days; and endovascular graft patency through 30 days, as evidenced by CT scan, angiography, or by duplex ultrasound in those patients experiencing renal failure and unable to undergo contrast-enhanced CT scan.

- *Treatment Success:* Technical success with no type I, type III, or type IV endoleaks at 12 months, no aneurysm-related major complications through 12 months, freedom from patency-related intervention through 12 months, no aneurysm enlargement greater than 0.5 cm through 12 months, and endovascular graft patency through 12 months as evidenced by CT scan, angiography or by duplex ultrasound in those patients experiencing renal failure and unable to undergo contrast-enhanced CT scan.

*Tortuosity of iliac arteries:* Tortuosity will be graded based upon the following:

None:	No tortuosity.
Mild:	Minimal tortuosity (less than one turn involving either external or common iliac artery).
Moderate:	Single turn involving either external or common iliac artery.
Severe:	Compound turns involving external and common iliac arteries.

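### The primary event is located in the internal iliac artery, so a later intervention for blockage of a Branch Graft segment feeding that artery can count as primary success

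*Protocol*

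**What the plan says.** **Purpose.** Protocol Section 4.1, repeated in Section 8.5, chooses 6-month freedom from patency-related intervention because the device "is intended to maintain blood flow to the internal iliac artery and minimize the risk of associated clinical symptoms with the need for reintervention".

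**The event.** Attachment B, Patency-Related Intervention, opens with "Secondary intervention to treat a > 60% stenosis of the internal iliac artery". The stenosis must be identified on imaging, confirmed by the core laboratory and associated with clinical symptoms. A note then sets the scope. It takes in narrowing that develops once the devices are in place: "this not only includes patients with internal iliac artery stenosis following successful placement of the Zenith® Branch Endovascular Graft-Iliac Bifurcation and covered bridging stent". It then adds blockage of the same vessel caused by technical failure, with a limit on timing and on consequence: "artery during the initial implant procedure that require secondary intervention for associated clinical symptoms".

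**Graft segments.** Attachment B has a separate term, Limb Occlusion (Branch Graft), for thrombus causing occlusion in any part of the graft: "i.e., common iliac segment, external iliac segment, or sidebranch segment), creating occlusion". The definition of patency-related intervention does not refer to it.

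**Neighbouring measures.** Under Success Measures, procedural success lists two separate components: "freedom from patency-related intervention through 30 days; and endovascular graft patency through 30 days". Treatment success does the same at 12 months. Same-side limb thrombosis is item 25 of the Morbidity Index, which is tested at 30 days. Branch vessel patency at 6 months is a descriptive secondary endpoint (Section 8.5).

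**The concern.** Blood reaches the internal iliac artery through the graft's common iliac segment, its sidebranch segment and the bridging stent. Symptomatic loss of patency in that path that needs reintervention is the failure the endpoint is meant to detect.

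Take a patient whose common iliac segment thromboses at month 3 and who has a secondary intervention. Inflow to the internal iliac artery is lost, but the intervention treats a graft segment. Unless a stenosis above 60% in the artery itself is also confirmed, the wording lets this patient count as free from patency-related intervention.

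An error of this kind goes in one direction, in favour of the device. Whether such a case counts would be left to judgment in a study that Section 8.2 describes as neither randomized nor blinded. The rate also matters beyond pass or fail, because Section 4.3.1 ties the choice of goal to labeling meant to guide the decision to sacrifice or preserve the artery.

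**Working it through.** **1. Which events the wording reaches**

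| Later event leading to secondary intervention | Inside the definition? |
|---|---|
| Internal iliac artery stenosis >60% after placement, symptomatic | Yes, stated |
| Internal iliac artery occlusion from technical failure at implant, symptomatic | Yes, stated |
| Later 100% occlusion of the internal iliac artery, symptomatic | Yes on a fair reading (100% exceeds 60%) |
| Narrowing inside the bridging stent | Arguable; not stated |
| Occlusion of the sidebranch segment after implant | Not stated; arguable if thrombus extends into the artery |
| Occlusion of the common iliac segment after implant | No, on the literal text |
| Occlusion of the external iliac segment | No; this segment does not feed the internal iliac artery |

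The gap is therefore one of location (graft rather than artery) for events after implant.

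**2. Whether another rule closes it.** Graft patency in Success Measures, descriptive branch vessel patency and Morbidity Index item 25 do not enter the primary count. An occlusion between day 31 and month 6 falls outside the 30-day safety test as well, so it enters neither hypothesis test.

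**3. The protocol's own power figure.** Inputs from Sections 4.3.1 and 8.10.1: goal 55%, assumed rate 83%, N=25, reject if the posterior 2.5th percentile exceeds 55%. The prior is not given in the text shown, so Beta(1,1) and Beta(0.5,0.5) are assumed. Both need at least 19 successes of 25.
- Power = P(X ≥ 19 | 25, 0.83) = 88.2%, against about 88.5% stated.
- Type I error = P(X ≥ 19 | 25, 0.55) = 2.58%, against 2.5% stated.

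The rule is reproduced. None of these figures depends on the anatomical wording.

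**4. The boundary at n=40.** Posterior is Beta(a + x, a + 40 − x).

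| Successes x | 2.5th percentile, a=1 | a=0.5 | Goal met? |
|---|---|---|---|
| 29 | 0.571 | 0.575 | Yes |
| 28 | 0.545 | 0.548 | No |

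Up to 11 failures are tolerated. A near-improper prior, Beta(0.001, 0.001), would move the threshold to 28.

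**5. Effect on the reported rate.** Each uncounted case adds 1/40 = 2.5 points. For an assumed 1 to 3 cases this is 2.5 to 7.5 points.

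**6. Effect on the decision at 83%.** With threshold 29, k miscounted cases reverse the result only if recorded successes lie between 29 and 28 + k. If recorded successes follow Binomial(40, 0.83):
- P(29) = 3.57%
- P(30) = 3.57% × (11/30) × (0.83/0.17) = 6.38%
- P(31) = 6.38% × (10/31) × (0.83/0.17) = 10.05%

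One case gives 3.6%, two give 3.57 + 6.38 = 9.9% (unrounded 9.95%), and three give 20.0%. The chance of meeting the goal at 83% is P(X ≥ 29) = 97.0%.

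**7. Effect on the false-positive rate (illustration).** Suppose freedom counted with the graft segments is exactly 55%, and the narrower wording adds 2.5, 5 or 10 points (assumed). The chance of passing at n=40 rises from 1.8% to 3.7%, 7.1% or 20.5%.

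**The case against.** Several points on the other side stand.

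- A reader might infer that the event covers stenosis alone and ignores occlusion. The text does not support this. The note in the definition includes implant-time occlusion of the artery and presents it as part of the same rule, so complete occlusion of the artery can be read as stenosis above 60%.
- Narrowing inside the bridging stent fits the existing wording reasonably well. Section 8.11.3 describes the stent as placed to preserve flow to that artery, and the definition speaks of stenosis following its placement. The clearest gap is the common iliac segment.
- A reader might infer that the protocol itself labels limb occlusion a device failure, or that such losses go unseen. Attachment B only defines the term, and the measures in step 2 would record the losses. Listing graft patency apart from patency-related intervention may be deliberate. None of this changes the primary count.
- The 55% goal in Section 4.3.1 comes from pelvic ischemic symptoms or complications in about 45% of patients after sacrifice of the artery. Counting interventions for leg symptoms alone would test an event for which that goal was not derived. This stands and limits the fix.
- The number of cases is assumed throughout. Parts of Sections 4.2 and 8.5 are redacted, although the definition itself shows no redaction.

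**Conclusion.** The concern holds as a gap of location. On the literal text, a secondary intervention after implant for stenosis or occlusion of the common iliac or sidebranch segment, and less clearly the bridging stent, can score as primary success even when it reflects lost flow to the internal iliac artery. No other text shown corrects this in the primary count.

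The bias can only raise the reported rate, by 2.5 points per case if all 40 patients are analysed. The protocol gives no frequency for such cases, so no corrected rate can be computed.

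A reader might infer that the pass/fail conclusion is unsafe. The documents do not show that. At the assumed 83%, one case has a 3.6% chance of reversing the result, and even three assumed cases leave it unchanged with about 80% probability. These figures assume a uniform or Jeffreys prior and take 83%, which Section 8.10.1 states as an arterial patency rate, as the rate of recorded success. The main harm is an overstated rate and an avoidable classification dispute. The definition should be amended, but the gap does not invalidate the design.

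**What to change.** Amend Patency-Related Intervention in Attachment B to cover a secondary intervention, at any time through 6 months for the primary endpoint, that meets all of the following:

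- it is for stenosis above 60% or occlusion, confirmed by the core laboratory;
- the site is the internal iliac artery, the bridging stent, or the sidebranch or common iliac segment of the Branch Graft;
- the lesion compromises internal iliac flow;
- it is associated with pelvic ischemic symptoms.

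The last condition keeps the event aligned with the basis of the 55% goal. Use the segment names of Limb Occlusion (Branch Graft). Carry the amended term into Success Measures, where it applies at 30 days and 12 months, and say there how it relates to the separate graft patency component.

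Add one sensitivity analysis of the primary endpoint that also counts interventions for occlusion of these segments done for limb symptoms only. Tabulate external iliac segment interventions separately.

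The cost is one amended definition, one extra analysis and a possibly slightly lower observed success rate. The core laboratory already determines occlusion by segment, so little new data should be needed. Confirming stenosis above 60% within a graft segment may need an added reading item. Make the change before 6-month outcomes are reviewed.
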